2.0 Background

Chronic nonbacterial osteomyelitis (CNO) is an autoinflammatory bone disease that mainly affects children and adolescents. Clinical presentations range from mild and sometimes limited unifocal disease to severe, chronically active or recurrent inflammation of multiple bones. The latter is referred to as chronic recurrent multifocal osteomyelitis (CRMO). Here we will use the term "CNO" to refer to the entire spectrum of this disease. CNO can be complicated by vertebral compression fractures, kyphosis, and leg length discrepancy when it is not recognized early or treated adequately. The diagnosis of CNO is made by excluding alternatives in the differential diagnosis including malignancy (leukemia, lymphoma, and primary or metastatic bone tumors), Langerhans cell histiocytosis, and infection. Clinical assessment in conjunction with serum inflammatory parameters and imaging studies, particularly magnetic resonance imaging (MRI), are crucial for the diagnosis and monitoring of disease activity of CNO¹.

Because of significant variation in clinical treatment practices among pediatric rheumatologists, standardized treatment regimens (consensus treatment plans, CTPs) have been developed within the Childhood Arthritis and Rheumatology Research Alliance (CARRA), a North American organization comprised of pediatric rheumatologists and researchers, for CNO patients with an NSAID-refractory course and/or with active spinal lesions². These CTPs provide an opportunity for pediatric rheumatologists to conduct comparative effectiveness research on CNO through prospective data collection. CRMO/CNO workgroup is comprised of pediatric rheumatologists from North America as well as international colleagues who are interested in collaborating in CNO research. Furthermore, risk factors of severe disease have been described by Wipff et al. based on a large retrospective cohort study³. Their results may be validated by an independent prospective cohort study. To date, there has been only one prospective study on CNO since its first description in 1972⁴. Therefore, we propose to establish this international registry of patients with CNO to accomplish above goals. Long-term

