3.0 Inclusion and Exclusion Criteria

Potential subjects will be identified by electronic medical record searches, clinic schedules, inpatient lists, and word of mouth recommendation. A member of the study team will review the potential subject's medical records to confirm diagnosis, language, and care plan. If eligible, the caregiver and subject will be approached for participation. Eligibility will be confirmed with the caregiver verbally prior to obtaining informed consent.

Inclusion Criteria

- Presence of bone edema on STIR or T2 fat saturation sequence on MRI within 12 weeks of enrollment (optional)
- Whole body imaging evaluation (either WB MRI or bone scintigraphy) is optional
- Bone biopsy to exclude infection or malignancy when indicated

Exclusion Criteria

- History of or current malignancy
- Current infectious osteomyelitis
- Contraindication to the selected treatment agent

Adults who are unable to consent and lack a legal guardian, wards of the state, and prisoners will be excluded.

Caregivers will be reporting about the subject's medical history therefore they are not considered study subjects.

As this is a multicenter international study, sites will use local language such as Turkish, German, Italian, etc.

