8.0 Study Endpoints

Primary Endpoint: Determine the effectiveness of commonly used medications in SOP for patients with CNO.

Clinical, laboratory and imaging results as well as PROs will be collected at each clinical visit after enrollment. Enrolled subjects will be stratified based on their past disease course, past treatment. Response to medication will be calculated based on previously described by Beck et al.⁵ and Zhao et al.² at clinical visits prior to and after starting a new medication for comparison. Clinical disease activity score (CDAS) comprised of patient pain (0-10), patient global disease activity per report (0-10), clinical lesion count by physician, will be used to determine response. >=50% of reduction of CDAS is defined as favorable response.

Secondary Endpoint: Determine the risk factors for patients with NSAID-refractory CNO.

Patients will be classified as NSAID responders (significant improvement of pain, focal exam, ESR, CRP, imaging within 6 months of NSAIDs treatment), NSAID non-responders (requiring >6 weeks of systemic glucocorticoid, disease modifying anti rheumatic drugs, TNF inhibitors, bisphosphonate) based on treating physician's assessment. Baseline demographic, clinical, laboratory, imaging results will be compared between two groups and odds ratio will be calculated. There is no safety endpoint because it is an observational study that does not pose any risk to subjects.

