11.0 Data Analysis/Management

We will use multivariable linear mixed-effects regression models, with each treatment as the dependent variable and person as the random effect, to estimate the average treatment effect, as well as the mean difference between groups, and any interactions as relevant to the particular Aim. The model will adjust for age, gender, lesion number and past medication use. The FDR will be used separately in each Aim to account for multiple pair comparisons, with FDR<0.1 considered significant.

Due to the rarity of CNO, we will enroll as many patients as possible to increase the power of this study to observe difference responses among treatments.

A random percentage of subject visits will be selected throughout the course of the study for data quality checks. A second study team member will review the data for accuracy and address any errors that are identified.

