13.0 Provisions to Monitor the Data to Ensure the Safety of Subjects

Due to the methods used to collect data, we do not expect adverse events related to the registry to occur. However, standardized severe adverse event (SAE) forms will be used to collect data for periodic update to the study group. Because this is an observational study, the medical decision is entirely determined by treating physician and not interfered by this registry.

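### The fixed covariate list for comparing physician-chosen drugs leaves out pre-drug CDAS and site, so differences in starting severity or between sites can be read as drug effects

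*Protocol*

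**What the plan says.** Aim 2 (Section 1.0) and the primary endpoint (Section 8.0) ask how well different drugs work in routine practice. Treatment is not randomised. Section 13.0 states that "the medical decision is entirely determined by treating physician and not interfered by this registry".

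Section 11.0 describes a linear mixed model "with each treatment as the dependent variable and person as the random effect" and then gives the adjustment set: "The model will adjust for age, gender, lesion number and past medication use". The list is stated flatly. It is not introduced as a set of examples, and no rule for extending it is given.

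Section 8.0 defines the outcome: "Clinical disease activity score (CDAS) comprised of patient pain (0-10), patient global disease activity per report (0-10), clinical lesion count by physician", with a fall of at least 50% counted as a favourable response. The score is taken "at clinical visits prior to and after starting a new medication for comparison", so the pre-drug value is collected by design. The same section says "Enrolled subjects will be stratified based on their past disease course, past treatment".

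On sites, Section 2.0 explains the consensus treatment plans with the words "Because of significant variation in clinical treatment practices among pediatric rheumatologists", and Section 3.0 says "As this is a multicenter international study, sites will use local language such as Turkish, German, Italian, etc". The analysis has no term for site, centre or country.

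**The concern.** With no randomisation, the covariate set is the main protection against confounding by indication. Two variables that could plausibly drive both drug choice and outcome are outside it.

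- **Pre-drug CDAS.** This is the starting value of the response measure. Lesion number overlaps with one of its three parts. Pain and patient global at drug start are unadjusted.
- **Site.** If prescribing habits differ between sites, and outcomes or scoring habits differ too, the drug comparison is partly a site comparison.

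A person random intercept does not help with either. It is assumed independent of treatment, so it absorbs correlation between visits without removing differences between patients or sites that go along with drug choice. At stake is the registry's main comparative result: a drug could look better or worse because of who received it, or where.

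This point takes CDAS response as the outcome. Section 11.0 names treatment as the dependent variable, which is a separate defect.

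**Working it through.** **What the document supplies.** It gives the covariate list, the random effect, the CDAS definition, the 50% threshold and the rule that physicians choose. It gives no effect size, SD, response rate or site-level data, so there is no stated figure to reproduce. Every number below rests on assumed inputs with no true drug difference. The numbers show mechanism and range, not the bias in this registry.

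**Step 1. Severity left out, continuous follow-up score.** To first order, bias = g × d. Here g is the outcome change per SD of omitted severity, and d is the difference in that severity between drug groups after the listed adjustment. If the log-odds of drug choice rise by h per SD of severity, and lesion number correlates r with severity, then d ≈ h(1 − r²). Assume g = 0.5 and h = 0.7, so g × h = 0.35. The simulation used 20 sites and 300 runs per setting.

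| r | 0.35(1 − r²) | Simulated bias, n=200 / n=500 (SD) | Significant at 5%, n=200 / n=500 |
|---|---|---|---|
| 0.3 | 0.319 | 0.288 / 0.299 | 45% / 85% |
| 0.6 | 0.224 | 0.209 / 0.209 | 27% / 55% |
| 0.8 | 0.126 | 0.113 / 0.122 | 15% / 24% |

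Lesion number shrinks the bias but does not remove it, even at r = 0.8.

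**Step 2. The 50% response.** Percent reduction is not adjustment for the starting level. Suppose mean follow-up is a + b × baseline. The mean fall is then 1 − b − a/baseline, which depends on baseline unless a = 0. Compare a baseline of 13 with one 3.5 points higher, 16.5. The last column is the simulated responder bias for the drug given to sicker patients (800 patients, 40 sites, drug choice following observed CDAS, lesion count and past medication unrelated to pain and global).

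| a, b | Fall at 13 | Fall at 16.5 | Responder bias (points) |
|---|---|---|---|
| 3, 0.2 | 1 − 5.6/13 = 56.9% | 1 − 6.3/16.5 = 61.8% | +7.00 |
| 1.5, 0.35 | 1 − 6.05/13 = 53.5% | 1 − 7.275/16.5 = 55.9% | +3.65 |
| 0, 0.5 | 50.0% | 50.0% | −0.05 |
| −1, 0.55 | 1 − 6.15/13 = 52.7% | 1 − 8.075/16.5 = 51.1% | −1.24 |

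On the defined endpoint the bias can therefore be positive, negative or negligible.

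**Step 3. Site left out.** Let severity play no part in drug choice, and let site prescribing and site outcome correlate at 0.5 in absolute value. The listed covariates then give a responder bias of 3.9 points in absolute size (about 23% significant at 5%). A random site effect leaves 2.1 points (about 10%), a reduction of (3.9 − 2.1)/3.9 = 46%. Adding each site's share of patients on the drug brings it to −0.04 (4%).

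**Step 4. Does adding pre-drug CDAS cure the severity problem?** It does if physicians act on the CDAS that is recorded. It does not if they act on underlying severity that CDAS measures with error. Assume 800 patients, CDAS SD about 4.7, 50–70% of its variance stable, and no site effects:

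| Outcome | Bias, listed covariates | Bias, pre-drug CDAS added |
|---|---|---|
| Follow-up CDAS | 1.0 to 2.1 | 0.4 to 0.8 |
| CDAS change | −0.04 to −0.08 | +0.44 to +0.77 |
| Responders (points) | −4.9 to −11.5 | −4.8 to −7.4 |

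A further run of this kind took follow-up CDAS from 1.7–2.3 down to 0.3–0.9. Once pre-drug CDAS is in the model, change and follow-up give the same drug coefficient, because they differ only by that covariate. Under this mechanism the change score without pre-drug CDAS is the nearly unbiased analysis; when choice follows the recorded CDAS, it is the biased one.

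**The case against.** **The model may already contain the pre-drug score.** A mixed model with person as random effect suggests several rows per patient, and the pre-drug visit could be an outcome row. That reading is possible, though Section 11.0 does not set it out. It would come close to a change-score comparison, which handles stable severity but not drug choice that follows the score of the day. Site differences in response would remain.

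**Covariates can be settled in a statistical analysis plan.** Often so, and one may exist. But Section 11.0 does not leave the set open. It states a list, and a plan that follows it exactly omits both variables.

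**Section 8.0 already stratifies.** Stratification by past course and past treatment is real control, and past medication use is in the model. Neither is current activity or site. A reader might infer that Sections 8.0 and 11.0 contradict each other over past disease course. They do not, since stratification needs no model term. Past course, the visit that supplies lesion number, and time since drug start are ordinary analysis-plan detail.

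**The site evidence is indirect.** This stands. Section 2.0 speaks of variation among physicians, and in the same sentence says treatment plans were developed in response. Section 3.0 mentions languages, not outcomes. Nothing shows that prescribing and outcome are linked by site.

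**The remedy is not a proven cure.** This stands too, as Step 4 shows.

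**A stronger inference.** A reader might conclude that the listed model will produce a false drug difference most of the time, or that adding pre-drug CDAS brings the bias to about zero. The documents support neither. False-positive rates depend wholly on assumed inputs, the highest arise on CDAS change (which Section 8.0 does not define as the response), and near-zero residual bias follows only if physicians choose on the recorded CDAS.

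**Conclusion.** The concern holds in a limited form. As written, Section 11.0 leaves pre-drug pain, pre-drug patient global and site unadjusted in a non-randomised drug comparison, and nothing else in the protocol controls them. Differences in starting severity or between sites can therefore be read as drug effects.

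The size and direction cannot be derived from the document. Under the assumptions shown, responder bias ran from −11.5 to +7.0 points and was close to zero in some settings. The severity part follows from the protocol's own definition of CDAS; the site part is plausible but indirectly supported. The change should be made because the omission is plain and the repair cheap. Confidence is medium.

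**What to change.** In Section 11.0, with CDAS response (at least 50% reduction, or follow-up CDAS) as the outcome and treatment as a predictor:

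1. Add CDAS at the last visit before drug start as a covariate.
2. Add site as a random effect, which keeps small sites and sites that use only one drug.
3. As a sensitivity analysis, add each site's share of patients on each drug, because a random site effect alone may remove only part of a site-linked bias.
4. As a second sensitivity analysis, report the comparison of CDAS change without pre-drug CDAS as a covariate.
5. State that the adjustment reduces confounding by measured severity and by site, but does not guarantee its removal if physicians choose on severity that CDAS captures imperfectly.

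Cost: a few more model parameters and no new data, since pre-drug CDAS is already needed to compute response and sites enter their own records. In simulations that also included past disease course, the SD of the responder estimate went from 3.9 to 3.7 points with 800 patients. With 200 patients at 20 sites it went from 7.5 to 7.6, or 8.3 with the site-share term. These figures also rest on assumed inputs.

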12.0 Confidentiality

Data will be kept in locked cabinets (paper forms) and/or in secure research drives and databases. Data will be identified with study codes and the link between study codes and subject identity will be kept separate from study data. Data being shared with other teams (see section 10) will be shared only as coded data without any linkers to preserve confidentiality.

Local sites will have data that are linked to a person's name, but the coordination center (Seattle Children's) will only receive coded samples without any links. Data (e.g. scans of the Case Report Forms) being sent and shared with the coordinating center will be sent using secure file sharing systems (eg: DropBox, REDCap) or by sending electronic copies via secure courier (eg: password protected CD or USB drive sent via tracked FedEx).

13.0 Provisions to Monitor the Data to Ensure the Safety of Subjects

Due to the methods used to collect data, we do not expect adverse events related to the registry to occur. However, standardized severe adverse event (SAE) forms will be used to collect data for periodic update to the study group. Because this is an observational study, the medical decision is entirely determined by treating physician and not interfered by this registry.

14.0 Withdrawal of Subjects

Subjects may be withdrawn if they become ineligible for inclusion, such as a misdiagnosis or subject becomes a foster child or prisoner. For subjects withdrawn for this reason, they (subject and/or caregiver) will be notified of the decision, and data collected prior to the withdrawal will be kept unless the caregiver otherwise requests that the data be removed from the study.

If withdrawn by the study team, further data will not be obtained past the date of withdrawal, but existing data will be kept and analyzed.

If withdrawn at the caregiver or subject's request, they will be asked if they would like for existing data to be removed from the database. If not, then existing study data will be kept and analyzed. If yes, data will be removed from the database at the caregiver and/or subject's request. In either case, additional data will not be collected.

If withdrawn from the study, the decision regarding existing data will be documented and filed with the original source documents. If the data is to be removed from the study, this work will also be documented.

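### Section 14 retains and analyses data from study-team withdrawals without excepting an overturned diagnosis, so patients found not to have CNO can stay in analyses meant for CNO patients

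*Protocol*

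**What the plan says.** Protocol Section 14 opens with withdrawal for ineligibility: "Subjects may be withdrawn if they become ineligible for inclusion, such as a misdiagnosis or subject becomes a foster child or prisoner". For these subjects, "data collected prior to the withdrawal will be kept unless the caregiver otherwise requests that the data be removed from the study". That paragraph does not say whether the retained data are analysed.

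The next paragraph covers every withdrawal made by the study team, which includes one for misdiagnosis. It states that "further data will not be obtained past the date of withdrawal, but existing data will be kept and analyzed". It makes no distinction by reason.

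Section 8 words its endpoints for people who have the disease. The primary endpoint is "Determine the effectiveness of commonly used medications in SOP for patients with CNO" and the secondary is "Determine the risk factors for patients with NSAID-refractory CNO". For the secondary endpoint, patients are classed as NSAID responders or non-responders, and "Baseline demographic, clinical, laboratory, imaging results will be compared between two groups and odds ratio will be calculated".

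Section 2 explains that "The diagnosis of CNO is made by excluding alternatives in the differential diagnosis", naming malignancy and infection among the alternatives. Section 3 lists as exclusions a past or present malignancy and "Current infectious osteomyelitis".

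**The concern.** Misdiagnosis differs in kind from the other two withdrawal reasons. A child who enters foster care, or a subject who is imprisoned, still has CNO, so using their data up to withdrawal is sound. A patient whose diagnosis is overturned never belonged to the population that Section 8 names. Section 14 nevertheless gives all three the same data rule.

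The event is foreseeable. The diagnosis rests on exclusion, Section 3 makes MRI evidence and whole-body imaging optional and asks for biopsy only when indicated, and Section 7 allows follow-up for up to 20 years. Records are reviewed for diagnosis before enrolment, but some diagnoses may still be revised later.

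The secondary endpoint has most at stake. If patients with another disease respond poorly to NSAIDs, they gather in the non-responder group and bring that disease's baseline features with them. Those features can then look like risk factors for refractory CNO.

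**Working it through.** **Text check.** A patient withdrawn for misdiagnosis falls under both of the first two paragraphs of Section 14. The first says the data are retained; the second says they are retained and analysed. Neither excepts an overturned diagnosis. Section 8 names the population but has no rule for dropping a patient later found not to have CNO. Section 11 lists adjustment covariates (age, gender, lesion number, past medication) and no restriction to confirmed CNO.

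**Size.** The protocol has no figure to reproduce: it gives no misdiagnosis rate, NSAID response rate or feature prevalence. Every input below is an assumption.

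- Share misdiagnosed, m: 2%, 5% or 10%.
- In CNO patients: 50% non-response; a baseline feature in 25% of responders and non-responders alike (true odds ratio 1.0); all classifiable.
- In misdiagnosed patients: non-response nr of 70% or 100%; share c that can be classed as responder or non-responder of 25%, 50% or 100%; feature prevalence p of 40% or 70%. That makes 2 × 3 × 2 = 12 combinations.

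Non-responders with the feature: 0.5(1−m)(0.25) + m·c·nr·p. Without it: 0.5(1−m)(0.75) + m·c·nr·(1−p). For responders, replace nr by 1−nr. The apparent odds ratio is the odds in non-responders divided by the odds in responders.

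Highest case at m = 5% (nr = 1, c = 1, p = 0.7):
- Non-responders: 0.11875 + 0.035 = 0.15375 with, 0.35625 + 0.015 = 0.37125 without; odds 0.4141.
- Responders: 0.11875 / 0.35625 = 0.3333.
- Odds ratio 0.4141 / 0.3333 = 1.242.

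Lowest case at m = 5% (nr = 0.7, c = 0.25, p = 0.4):
- Non-responders: 0.12225 / 0.3615 = 0.3382.
- Responders: 0.12025 / 0.3585 = 0.3354.
- Odds ratio 1.008.

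All 12 combinations at m = 5%:

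| nr | p | c = 25% | c = 50% | c = 100% |
|---|---|---|---|---|
| 70% | 40% | 1.008 | 1.016 | 1.030 |
| 70% | 70% | 1.025 | 1.048 | 1.090 |
| 100% | 40% | 1.021 | 1.040 | 1.078 |
| 100% | 70% | 1.063 | 1.124 | 1.242 |

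Across the three misdiagnosis shares:

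| m | Lowest | Second highest | Highest |
|---|---|---|---|
| 2% | 1.003 | 1.049 | 1.096 |
| 5% | 1.008 | 1.124 | 1.242 |
| 10% | 1.017 | 1.255 | 1.490 |

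With nr = 50%, as in CNO, both groups contain the same mixture and the odds ratio is 1.000.

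**Drug comparisons.** Assume favourable response of 50% and 70% on two drugs, with misdiagnosed patients spread evenly. The difference becomes 20(1−m) points: 19.6, 19.0 and 18.0 at 2%, 5% and 10%. The even spread matters. If all misdiagnosed patients sat in the better of two equal groups and 0% to 20% of them responded, then at m = 5% that group would read 0.9 × 70 + 0.1 × (0 to 20) = 63 to 65, a difference of 13 to 15 points. Nothing in the protocol suggests such concentration.

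**The case against.** The best defence is that Section 14 is about handling records, not about defining an analysis set. It does not say which analysis is meant, and the word could cover descriptive use only. The pre-screening rule in Section 29 likewise keeps coded reasons for ineligibility for analysis, although those people never enter an endpoint analysis. Section 8's wording points to CNO patients only, and a statistical analysis plan, not shown here, could define a confirmed-CNO set. This has weight: the protocol permits the inclusion and does not compel it. It does not dispose of the point, because the protocol states a positive rule without qualification, and a later plan that excluded these patients would have to narrow it.

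Three stronger readings are tempting and are not supported:

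- *That the two paragraphs contradict each other.* The first offers removal on request and the second does not mention it, but Section 10 gives caregivers and subjects a general written right to removal, so the difference is modest. On analysis, the first paragraph is silent rather than opposed.
- *That the results will be materially distorted.* All inputs are assumed, and most combinations give a small shift. The worst case needs every misdiagnosed patient to be both classifiable and a non-responder, with 70% carrying the feature.
- *That a rate of falsely declared risk factors can be worked out from the FDR threshold in Section 11.* That rule is stated for multiple pair comparisons, and the protocol gives no number of candidate features.

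It is also fair to say that excluding patients on later information can itself bias the comparison, if diagnoses are re-examined more often in non-responders.

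**Conclusion.** The point holds as a minor one. Section 14 names misdiagnosis, groups it with reasons that leave the diagnosis intact, and applies to all of them a rule that existing data are analysed. Patients found not to have CNO can therefore stay in analyses worded for CNO patients.

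The size of the effect cannot be derived from the protocol. On the assumptions shown, it is small in most scenarios and absent if misdiagnosed patients respond to NSAIDs as CNO patients do. It becomes appreciable only if they are common and concentrated among classifiable non-responders. Drug comparisons are little affected provided misdiagnosis is similar across drugs.

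**What to change.** In Section 14, separate misdiagnosis from the administrative reasons and state that:

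- the record is kept unless removal is requested, in line with Section 10;
- patients with a confirmed alternative diagnosis are excluded from the main analyses for Aims 1 to 3;
- their number, final diagnosis and NSAID-response group are reported;
- one sensitivity analysis includes them;
- patients withdrawn for administrative reasons are still analysed up to withdrawal.

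The cost is one or two sentences and slightly fewer analysed patients. The exclusion relies on information that may come to light more often in non-responders; the sensitivity analysis shows that effect but does not remove it. Misdiagnoses that are never detected remain in the data either way.
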